9.4.4 SAFETY ANALYSES

The incidence of treatment-emergent adverse events will be summarized by system organ class and/or preferred term, type of adverse event, severity (based on NCI CTCAE v4.03 grades), and relation to study treatment using the safety population. The most severe grade per patient will be reported. Elapsed days of toxicity will be summarized with descriptive statistics. Adverse events leading to premature discontinuation from the study intervention and serious treatment-emergent adverse events will be presented in tabular form. Changes in laboratory values and vital signs will be summarized with descriptive statistics. The incidence of concomitant medications will be summarized.

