- e) **Thyroid Disorders:** Pembrolizumab can cause thyroid disorders, including hyperthyroidism, hypothyroidism and thyroiditis. Hyperthyroidism occurred in 96 (3.4%) of 2799 patients receiving pembrolizumab, including Grade 2 (0.8%) and Grade 3 (0.1%) hyperthyroidism. The median time to onset was 1.4 months (range: 1 day to 21.9 months), and the median duration was 2.1 months (range: 3 days to 15.0+ months). Hyperthyroidism led to discontinuation of pembrolizumab in 2 (<0.1%) patients. Hyperthyroidism resolved in 71 (74%) of the 96 patients. Hypothyroidism occurred in 237 (8.5%) of 2799 patients receiving pembrolizumab, including Grade 2 (6.2%) and Grade 3 (0.1%) hypothyroidism. The median time to onset was 3.5 months (range: 1 day to 18.9 months), and the median duration was not reached (range: 2 days to 27.7+ months). Hypothyroidism led to discontinuation of pembrolizumab in 1 (<0.1%) patient. Hypothyroidism resolved in 48 (20%) of the 237 patients. The incidence of new or worsening hypothyroidism was higher in patients with HNSCC occurring in 28 (15%) of 192 patients receiving pembrolizumab, including Grade 3 (0.5%) hypothyroidism. Of these 28 patients, 15 had no prior history of hypothyroidism. Thyroiditis occurred in 16 (0.6%) of 2799 patients receiving pembrolizumab, including Grade 2 (0.3%) thyroiditis. The median time of onset was 1.2 months (range: 0.5 to 3.5 months).
- f) **Type 1 Diabetes mellitus:** Pembrolizumab can cause type 1 diabetes mellitus, including diabetic ketoacidosis, which has been reported in 6 (0.2%) of 2799 patients receiving pembrolizumab. Monitor patients for hyperglycemia or other signs and symptoms of diabetes. Administer insulin for type 1 diabetes and withhold pembrolizumab and administer antihyperglycemics in patients with severe hyperglycemia.
- g) **Immune-Mediated Nephritis and Renal Dysfunction:** Pembrolizumab can cause immune-mediated nephritis. Monitor patients for changes in renal function. Nephritis occurred in 9 (0.3%) of 2799 patients receiving pembrolizumab, including Grade 2 (0.1%), Grade 3 (0.1%), and Grade 4 (<0.1%) nephritis. The median time to onset was 5.1 months (range: 12 days to 12.8 months), and the median duration was 3.3 months (range: 12 days to 8.9+ months). Eight (89%) of the 9 patients received systemic corticosteroids, with 7 of the 8 receiving high-dose corticosteroids for a median duration of 15 days (range: 3 days to 4.0 months) followed by a corticosteroid taper.

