should be sent to the subject (or the subject's legal guardian) requesting contact with the clinic. If a subject is discontinued from study treatment because of an AE considered to be related to study treatment and the event is ongoing 30 days after the last dose of study treatment, the event must be followed until resolution or determination by the investigator that the event has become stable or irreversible.

If a subject withdraws consent to participate in the study, the reason for withdrawal will be documented, no further study procedures or assessments will be performed, and no further study data will be collected for this subject, other than the determination of survival status from public records such as government vital statistics or obituaries.

Patients that withdraw from study treatment (but not their consent for follow-up) for reasons other than progression will continue to have scans per study calendar until PD is noted.

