8.2 SAFETY AND OTHER ASSESSMENTS

An investigator who is a qualified physician will evaluate all adverse events according to the NCI Common Terminology for Adverse Events (CTCAE), version 4. Any adverse event which changes CTCAE grade over the course of a given episode will have each change of grade recorded on the adverse event case report forms/worksheets. All adverse events regardless of CTCAE grade must also be evaluated for seriousness. For studies in which multiple agents are administered as part of a combination regimen, the investigator may attribute each adverse event causality to the combination regimen or to a single agent of the combination. In general, causality attribution should be assigned to the combination regimen (i.e., to all agents in the regimen). However, causality attribution may be assigned to a single agent if in the investigator's opinion, there is sufficient data to support full attribution of the

adverse experience to the single agent. The details of classification of adverse events is provided in Section 8.3.3

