8.3.4.2 End of treatment and premature withdrawal visit

Required observations following the completion of protocol therapy: Follow-up visits may be performed +/- 7 days from the targeted study visit date. Laboratory evaluations may be collected up to 24 hours prior to study visit without being a deviation.

Patients will be followed for survival and progression every 3 months for 2 years, every 6 months for 3 years and yearly until death. Follow-up will be performed using telephone contact, correspondence with treating physicians, and death records as necessary to update vital status.

Adverse events	Capture all AEs observed for 30 days after last dose of treatment. After 30 days, only SAEs that are at least possibly attributed to the study drug are required to be captured
Concomitant medications	Capture all concomitant medications for 30 days after last dose of treatment or until a new treatment is started, whichever occurs first.

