9.4 STATISTICAL ANALYSES

9.4.1 GENERAL APPROACH

Continuous variables will be summarized using descriptive statistics such as mean, standard deviation, median, minimum, and maximum. Categorical variables will be summarized by count and proportion.

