9.4.3 ANALYSIS OF THE SECONDARY ENDPOINT(S)

The secondary efficacy endpoints (DCR, PFS and OS) will be summarized descriptively using the mITT population.

DCR

DCR is defined as the proportion of patients with RECIST disease control (CR, PR, or SD). All patients that do not meet the criteria for an objective response by the analysis cutoff date will be considered non-responders. A binomial proportion with 95% exact confidence interval will be reported.

PFS

PFS will be defined as the time from treatment initiation to the date of first documentation of disease progression or death due to any cause in the absence of documented progression. For patients who discontinue study treatment due to reasons other than progression or death, the patient will be censored at their last radiographic assessment for progression. Cumulative PFS will be descriptively summarized over time with the method of Kaplan-Meier.

OS

OS will be defined as the time from treatment initiation to the date of death due to any cause. Cumulative OS will be descriptively summarized over time with the method of Kaplan-Meier.

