11.6 ROUTINE ADVERSE EVENT REPORTING

For non-serious Adverse Events, documentation must begin from the time the informed consent document is signed through the 30-day follow-up period after study drug is discontinued.

Collected information should be recorded in the electronic/Case Report Forms (eCRF/CRF) for that subject. A description of the event, its severity or toxicity grade (according to [NCI's](#)

Common Toxicity Criteria (CTCAE)4.04), onset and resolved dates (if applicable), and the relationship to the study drug should be included. Documentation should occur in real time. The principal investigator has final responsibility for determining the attribution of the event as it is related to the study drug.

For any experience or condition that meets the definition of a serious adverse event (SAE), recording of the event must begin after signing of the informed consent and continue through the 30-day follow-up period after treatment is discontinued.

Investigators must report to the DSMC any serious adverse events (SAE), whether or not they are considered related to the investigational agent(s)/intervention (21 CFR 312.64). SAEs must be reported via an OnCore SAE Report within 24 hours of learning of the event.

An adverse event is considered **serious** if it results in ANY of the following outcomes:

- Death
- A life-threatening adverse event
- An adverse event that results in inpatient hospitalization OR prolongation of existing hospitalization for ≥ 24 hours
- A persistent or significant incapacity or substantial disruption of the ability to conduct normal life functions
- A congenital anomaly/birth defect.
- Important Medical Events (IME) that may not result in death, be life threatening, or require hospitalization may be considered serious when, based upon medical judgment, they may jeopardize the patient or subject and may require medical or surgical intervention to prevent one of the outcomes listed in this definition. (FDA, [21 CFR 312.32](#); [ICH E2A](#) and [ICH E6](#)).

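### Section 9.4.4 summarises elapsed days of toxicity without saying how unresolved events count, which would bias durations short for toxicities that mostly do not resolve

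*Combined protocol and SAP*

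**What the plan says.** The only statement on toxicity duration is in Section 9.4.4: "Elapsed days of toxicity will be summarized with descriptive statistics". Section 9.4.1 gives the general meaning: "Continuous variables will be summarized using descriptive statistics such as mean, standard deviation, median, minimum, and maximum".

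Other sections show that some events will have no end date:

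- Section 11.6 lists what is recorded for each event: "onset and resolved dates (if applicable), and the relationship to the study drug should be included".
- Section 8.3.4.2 limits routine collection: "Capture all AEs observed for 30 days after last dose of treatment". After that, only serious events at least possibly attributed to study drug are required.
- Section 7.2 extends follow-up for related events that led to treatment discontinuation and are ongoing at 30 days: "the event must be followed until resolution or determination by the investigator that the event has become stable or irreversible". The second of those endings gives no resolved date.

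Section 8.2 adds: "Any adverse event which changes CTCAE grade over the course of a given episode will have each change of grade recorded". Nothing says whether elapsed days are counted per episode or per grade segment. Section 9.4.8 plans no individual listings. Kaplan-Meier is specified only for PFS and OS in Section 9.4.3.

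**The concern.** Elapsed days require an onset and an end. An event still ongoing at last contact has only a lower bound for its duration. If the analyst takes a plain mean or median, such an event is either left out or treated as if it ended on the last recorded day. Both choices shorten the reported duration, and the shortening grows with the share unresolved.

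The protocol's own background shows that this share can be large. Section 2.3.1.2 reports for pembrolizumab: "Hypothyroidism resolved in 48 (20%) of the 237 patients". It gives the median duration there as not reached, with a range whose upper end is marked as censored. A plain median from this trial could not be set beside that figure.

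Describing the safety profile is a Phase 1 secondary objective (Section 3), and how reversible the toxicities are is part of that description. If the convention is chosen after the data are seen, lasting endocrine toxicity could look transient.

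**Working it through.** The plan states no figure for toxicity duration, so there is none to reproduce. The check asks how far a plain median would fall below the true one.

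**Inputs from the documents.** Resolved counts for pembrolizumab come from Section 2.3.1.2. Patient numbers come from Section 9.2 (Phase 1 up to 18, Phase 2 44, so 62 in all).

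**Assumptions.** The documents give neither the distribution of durations nor the follow-up after onset. Each scenario is calibrated so that the share resolved by the end of observation, p, equals the protocol's figure. That figure reflects the follow-up of the source studies, not of this trial.

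**Two conventions.** (a) Ongoing events are dropped. (b) Ongoing events are counted as ended at last observation.

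**Closed form.** Take exponential durations with rate λ and equal follow-up C, so p = 1 − exp(−λC). The true median is ln 2/λ.

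- (a) The median m among resolved events solves 1 − exp(−λm) = p/2, so reported/true = −ln(1 − p/2)/ln 2.
- (b) The median of min(T, C) is min(ln 2/λ, C), so reported/true = min(1, −ln(1 − p)/ln 2).

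For hypothyroidism, p = 48/237 = 0.203:

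- (a) −ln(0.899)/0.693 = 0.107/0.693 = 0.15
- (b) −ln(0.797)/0.693 = 0.226/0.693 = 0.33

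**Sensitivity.** Simulations used Weibull shapes 0.7, 1 and 1.5, each with equal or uniformly spread follow-up. Entries are reported/true median; 1.00 means no bias.

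| Toxicity | Resolved | (a) closed form | (b) closed form | (a) range | (b) range |
|---|---|---|---|---|---|
| Hypothyroidism | 48/237 = 20% | 0.15 | 0.33 | 0.07–0.34 | 0.17–0.47 |
| Hypophysitis | 7/17 = 41% | 0.33 | 0.77 | 0.21–0.56 | 0.43–0.84 |
| Nephritis | 5/9 = 56% | 0.47 | 1.00 | 0.34–0.69 | 0.59–1.00 |
| Pneumonitis | 55/94 = 59% | 0.50 | 1.00 | 0.37–0.72 | 0.62–1.00 |
| Hyperthyroidism | 71/96 = 74% | 0.67 | 1.00 | 0.56–0.84 | 0.77–1.00 |
| Hepatitis | 15/19 = 79% | 0.72 | 1.00 | 0.63–0.88 | 0.82–1.00 |
| Colitis | 41/48 = 85% | 0.80 | 1.00 | 0.73–0.92 | 0.87–1.00 |

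If follow-up instead ends at a constant hazard and durations are exponential, both conventions give a ratio equal to the resolved share: 0.20 for hypothyroidism, 0.85 for colitis.

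**Mean under (b).** With exponential durations and equal follow-up, E[min(T, C)] = p/λ, so the mean falls to the resolved share of the true mean even where the median is unbiased: 0.59 for pneumonitis, 0.85 for colitis.

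**Kaplan-Meier on the same simulated data.** The estimate was the true median or not reached. For hypothyroidism it was not reached in every scenario, consistent with Section 2.3.1.2. For hypophysitis it was not reached with equal follow-up and 1.00 with uniform follow-up. For the other five it was 1.00.

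**Number of events.** Applying the monotherapy rate to this combination for scale only, hypothyroidism is expected in 44 × 237/2799 = 3.7 patients, or 62 × 237/2799 = 5.2. All seven toxicities together (520 of 2,799) give about 8 of 44 or 12 of 62.

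**The case against.** The strongest reply is that the plan is silent rather than wrong. Section 9.4.4 says only that the statistics are descriptive, and the list in Section 9.4.1 is illustrative. Section 9.4.3 itself treats Kaplan-Meier as description: "Cumulative PFS will be descriptively summarized over time with the method of Kaplan-Meier". A reader might infer that the planned analysis cannot accommodate ongoing events. The documents do not support that, because an analyst could censor without departing from the text. What remains is that nothing requires it, and the statistics named in Section 9.4.1 do not censor.

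A reader might also infer that long-lasting immune toxicities in general will be reported as far shorter than they are. That does not follow. The size depends on an unstated convention and on the share resolved. With equal follow-up and convention (b), the medians for nephritis and pneumonitis are unbiased and hypophysitis is about 0.77 of the truth. Colitis, hepatitis and hyperthyroidism, with 74% to 85% resolved, are affected much less.

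Follow-up is also longer than the 30-day limit suggests. The limit runs from the last dose, not from onset, and treatment may be long. Related serious events are captured later, and Section 7.2 extends follow-up for some others. This helps little where censoring is heaviest: Section 2.3.1.2 reports that hypothyroidism led to discontinuation in 1 patient, against 237 affected.

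Finally, the counts are small and nothing is decided on duration. Incidence, worst grade, relatedness, serious events and discontinuations are reported separately, and dose-limiting toxicity is judged by counts within 21 days. This stands in full and limits the point to a reporting correction.

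**Conclusion.** The point holds in a limited form. The plan has no rule for events without a resolved date, although it foresees them. Under either simple convention, the median duration of hypothyroidism would be about 0.07 to 0.47 of its true value. For events that mostly resolve the bias is smaller or absent; colitis gives 0.73 to 1.00.

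These ratios rest on assumed duration distributions and follow-up patterns, and on pembrolizumab monotherapy data carried over to the combination. The direction for hypothyroidism was the same in every scenario; the exact size is not known.

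The consequence is confined to a descriptive safety summary with few events. It would be going too far to infer that dose selection, the response analysis or the main toxicity tables are compromised, since none of them uses elapsed days.

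**What to change.** Replace the sentence in Section 9.4.4 with:

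> For each toxicity episode (onset to resolution, across grade changes), the number and percentage unresolved at last follow-up or death will be reported. Time to resolution will be summarised by Kaplan-Meier, with ongoing events censored at last follow-up, where event numbers allow. Death before resolution will be reported separately or treated as a competing event. Any summary of elapsed days restricted to resolved episodes will be labelled as such.

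Defining the episode settles the unit left open by the recording of each grade change. Death needs its own handling because treating it as ordinary censoring overstates the probability of resolution when deaths are frequent.

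The cost is slightly more analysis. Onset and resolved dates are already collected, and Kaplan-Meier is already planned for PFS and OS. For rare toxicities the estimate may be uninformative, and the count of unresolved events will then carry the message.

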9.4.5 BASELINE DESCRIPTIVE STATISTICS

Descriptive statistics will be presented to characterize the patient population. No inferential statistics will be conducted since this is a one-arm trial.

9.4.6 PLANNED INTERIM ANALYSES

No interim efficacy analyses are planned.

9.4.7 SUB-GROUP ANALYSES

No subgroup analyses are planned.

9.4.8 TABULATION OF INDIVIDUAL PARTICIPANT DATA

Individual participant data will not be listed.

9.4.9 EXPLORATORY ANALYSES

10 SUPPORTING DOCUMENTATION AND OPERATIONAL CONSIDERATIONS

10.1 REGULATORY, ETHICAL, AND STUDY OVERSIGHT CONSIDERATIONS

10.1.1 INFORMED CONSENT PROCESS

Potential subjects will be recruited from patients seen in the Clinical Cancer Center at

University of Iowa Hospitals and Clinics who appear to be eligible for the study. A member of the research team will meet with the patient to go over the informed consent document and answer any questions they may have. Other potential treatment options, whether investigational or standard of care, will be discussed with the patient. The patient will be given the time they need to make their decision; they are encouraged to discuss it with their family and/or friends. If the patient decides to participate, they will need to sign the consent form during one of their clinic visits. No study-specific procedures will be performed before the informed consent document is signed.

To avoid coercion, potential patients will be informed that they are free to refuse to participate in the trial, and that refusing to participate will not affect the availability of future medical care at UIHC. A copy of the signed informed consent document will be given to the patient.

10.1.2 TABULATION OF INDIVIDUAL PARTICIPANT DATA

The investigator must maintain detailed records of all trial participants who are enrolled in the trial or who undergo screening. Source documents include, but are not limited to, patient medical records and investigator's patient trial files, as well as all test results.

The following minimum information should be entered into the enrolled patient's source documents:

- The date the patient entered the trial and the patient number
- The trial protocol number
- The date that informed consent was signed
- Evidence that the patient meets trial eligibility requirements (eg, medical history, trial procedures, evaluations)
- The dates of all trial-related patient visits
- Evidence that trial-required procedures and/or evaluations were completed
- Use of any concurrent medications
- Documentation of trial medication accountability
- Occurrence and status of any AEs
- The date the patient exited the trial, and a notation as to whether the patient completed the trial or was discontinued early, including the reason for discontinuation
- Any deviations from the protocol

10.1.3 CONFIDENTIALITY OF TRIAL DOCUMENTS AND SUBJECT RECORDS

The investigator must assure that subjects' anonymity will be maintained and that their identities are protected from unauthorized parties. On CRFs or other documents, subjects will be identified by identification codes and not by their names. The investigator should keep a subject enrollment log showing codes, names, and addresses. The investigator should maintain documents (eg, subjects' written consent forms) in strict confidence.

All tumor scans, research samples, photographs, and results from examinations, tests, and procedures may be sent to Exelixis and its partners or designees for review.

10.1.4 PUBLICATIONS OF DATA AND PROTECTION OF TRADE SECRETS

The Principal Investigator (Protocol Chair) holds the primary responsibility for publication of the study results; provided that the PI will provide Exelixis with a copy of any proposed publication or release: (a) for abstracts, slide presentations or posters, at least five (5) business day prior to submission (in the case of abstracts) or first public presentation (in the case of slide presentations and posters); and (b) at least thirty (30) days in advance of first submission and each subsequent submission in the case of manuscripts and also comply with any provisions regarding publication that are agreed to between the PI's institution (eg, institution name.) and Exelixis, Inc. in the Clinical Trial Agreement related to this study.

11.0 TRIAL-SPECIFIC DATA AND SAFETY MONITORING PLAN

Type of Clinical Trial:

 Investigator-initiated (UI/HCCC)	 Investigator-initiated, participating site
 Pilot study	 Phase I
 Phase I/II	 Phase II
 Phase III	 Compassionate-use/Expanded Access
 Interventional Treatment	 Interventional Non-Treatment
 Non-Interventional	

Study risk-level:

- Level 1—low risk of morbidity or death, * <1% of death or any adverse event
- Level 2—risk of death* <1% or any adverse event 1% – 5%
- Level 3—risk of death* 1% – 5% or grade 4 – 5 SAE 1% – 5%
- Level 4—risk of death* >5% or grade 4 – 5 SAE >5%
- Drugs being used on a “compassionate” basis

* *Risk of death* refers specifically to 100-day treatment-related mortality

Reporting and Monitoring Requirements:

All institutional investigator initiated trials (IITs), regardless of assigned risk level are subject to routine DSMC monitoring activities which may include but are not limited to review of signed consent documents, eligibility and adverse event reporting.

All institutional IITs have the following **reporting requirements** as part of their DSMP:

- Register all subjects in HCCC’s Clinical Trial Management System, OnCore
- Document Adverse Events
- Document protocol deviations
- Provide an annual progress report to the DSMC via OnCore data export

Selected monitoring strategy based on risk-level:

Risk Level 4

Interventional treatment trials involving investigational agents or devices with a risk of death* (>5% or grade 4 – 5 SAE >5%), e.g. all investigator initiated INDs, most Phase I/II trials, gene therapy, gene manipulation or viral vector systems high-risk clinical procedures if performed solely for research purposes. The use of a new chemical or drug for which there is limited or no available safety data in humans.

Study Safety Review

An independent study monitor and/or the DSMC Chair (or designee), will review study data (provided by the PI/available in OnCore) and communicate with the PI at least biannually. A copy of this communication will be forwarded to the DSMC and PRMC Chairs.

Additional Reporting Requirements:

- A scanned copy of the completed eligibility checklist, with screening information and PI signature, will be attached in OnCore for ongoing review by DSMC staff.

- Serious adverse events will be entered directly into an OnCore SAE report by the research team. OnCore will send an automatic notification to the DSMC Chair/acting Chair and staff for review.
- The DSMC utilizes a risk-based monitoring approach. The trial's research records will be monitored at minimum twice per year. Monitoring may be done more frequently depending on the protocol, risks to subjects, reported serious/adverse events, patient population and accrual rate. Records for a minimum of 25% of subjects will be monitored for the entire study.

Monitoring will involve the following:

- review eligibility of patients accrued to the study,
- check for the presence of a signed informed consent,
- determine compliance with protocol's study plan,
- determine whether SAEs are being appropriately reported to internal and external regulatory agencies,
- compare accuracy of data in the research record with the primary source documents,
- review investigational drug processing and documentation,
- assess cumulative AE/SAE reports for trends and compare to study stopping rules.

Routine Adverse Event Reporting

For non-serious Adverse Events, documentation must begin from the time the informed consent document is signed through the 30-day follow-up period after study drug is discontinued.

Collected information should be recorded in the electronic/Case Report Forms (eCRF/CRF) for that subject. A description of the event, its severity or toxicity grade (according to [NCI's Common Toxicity Criteria \(CTCAE\)](#)), onset and resolved dates (if applicable), and the relationship to the study drug should be included. Documentation should occur in real time. The principal investigator has final responsibility for determining the attribution of the event as it is related to the study drug.

Serious Adverse Event Reporting

For any experience or condition that meets the definition of a serious adverse event (SAE), recording of the event must begin after signing of the informed consent and continue through the 30 day follow-up period after treatment is discontinued.

Investigators must report to the DSMC any serious adverse events (SAE), whether or not they are considered related to the investigational agent(s)/intervention (21 CFR 312.64). SAEs must be reported via an OnCore SAE Report within 24 hours of learning of the event.

An adverse event is considered **serious** if it results in ANY of the following outcomes:

1. Death
2. A life-threatening adverse event
3. An adverse event that results in inpatient hospitalization OR prolongation of existing hospitalization for ≥ 24 hours
4. A persistent or significant incapacity or substantial disruption of the ability to conduct

normal life functions

5. A congenital anomaly/birth defect.
6. Important Medical Events (IME) that may not result in death, be life threatening, or require hospitalization may be considered serious when, based upon medical judgment, they may jeopardize the patient or subject and may require medical or surgical intervention to prevent one of the outcomes listed in this definition. (FDA, [21 CFR 312.32](#); [ICH E2A](#) and [ICH E6](#)).

FDA Reporting Requirements (for Sponsor-Investigators)

It is the responsibility of the IND sponsor-investigator to comply with IND safety reporting as set forth in the Code of Federal Regulations, [Section 312.32](#). This responsibility includes providing an annual IND report to the FDA.

All IND safety reports must be submitted on [Form 3500A](#) and be accompanied by [Form 1571](#). The type of report (initial or follow-up) should be checked in the respective boxes on Forms 3500A and 1571. See [Instructions for completing Form 3500A. Please note all](#) instance of UIHC, location, and faculty / staff should be redacted from supporting documentation and the 3500A.

The submission must be identified as:

- “IND safety report” for 15-day reports, or
- “7-day IND safety report” for unexpected fatal or life-threatening suspected adverse reaction reports, or
- “Follow-up IND safety report” for follow-up information.

For detailed explanation of the above definitions, requirements, and procedures related to IND application safety reports and the responsibilities of IND applications sponsors with regard to such reporting, refer to [Guidance for Industry and Investigators: Safety Reporting Requirements for INDs and BA/BE Studies \(PDF - 227KB\)](#)

In addition to completing appropriate patient demographic and suspect medication information, the report should include the following information within the Event Description (section 5) of the MedWatch 3500A form:

- Treatment regimen (dosing frequency, combination therapy)
- Protocol description (and number, if assigned)
- Description of event, severity, treatment, and outcome, if known (grading the event per CTCAE)
- Supportive laboratory results and diagnostics
- Sponsor-Investigator’s assessment of the relationship of the adverse event to each investigational product and suspect medication

Data Monitoring and Management

Subject Registration

All studies that undergo PRMC review and/or utilize HCCC Clinical Research Services (CRS) resources are required to register subjects in OnCore. Each subject registration includes the following:

- The subject’s IRB approved (version date) consent form and the date of their consent.

- Date of eligibility and eligibility status (eligible, not eligible)
- On study date and subject's disease site (and histology if applicable)
- On treatment date (if applicable)

All subject registration information is expected to be entered into OnCore within **2 (two) business days** after the subject's study visit.

Subject Data

For HCCC investigator-initiated trials, research staff are responsible for entering subject study data (data collection) into OnCore electronic case report forms (eCRFs). These eCRFs must be approved by the PI and statistician prior to study activation to ensure sufficient and necessary data acquisition. All information entered into eCRFs will be traceable to the source documents which are generally maintained in the subject's file.

eCRF data entry needs to be timely and should be entered into OnCore as soon as possible but no later than **14 (fourteen) business days** after the subject's visit, including adverse events, tumor measurements, administration of study medication, concomitant medications, labs, and vitals. Physical exam assessments must be entered no later than **14 (fourteen) business days** following completion of the physician's clinic note in the medical record.

Timely data entry facilitates remote monitoring of data, allows the data to progress appropriately through the data cleaning process, and helps prevent a backlog of data queries.

Forms Monitoring

OnCore eCRF data are monitored on a routine basis (dependent on accrual) to ensure all data are entered completely, accurately, and within time requirements outlined above. The assigned DSMC monitor will coordinate and complete the data monitoring review. When the time comes to monitor a study (based on patient accrual and assigned risk level of trial) the monitor arranges for a selection of cases to be reviewed from among the subjects registered in OnCore. As part of the forms monitoring process, the assigned monitor will issue queries via OnCore (linked to the eCRF) to resolve missing, incomplete, and/or incorrect information. A member of the research team is expected to respond to these monitoring queries within **14 (fourteen) business days**.

The monitoring process can often identify misunderstandings or deficiencies in the written, research protocol requirements earlier in the study process and thereby improve data quality and reduce rework.

Final Reports

A summary of each subject's data record is continually available to the PI, research staff, and DSMC from OnCore's Biostat Console. The availability of this information is a valuable tool for the preparation of final reports and manuscripts as well as ongoing deficiency reports.

